### 12.1.3 Structural Outcomes

1	Definition Number	3.1
2	Definition Name	Opioid prescriptions from multiple prescribers or pharmacies
3	Data Sources	Prescription drug monitoring program; CDC standards for MME; census data for population estimates
4	Other Available Data for Additional or State-Specific Analyses	Claims (Medicaid in Kentucky, all-payer in Massachusetts and New York, Ohio can combine Medicaid and OhioMHAS data)—these are inferior to PMP because they lack cash payments)
5	Primary Outcome Measure	Count of individuals with an opioid prescription from $\geq 4$ providers or $\geq 4$ pharmacies in a quarter
6	Population Size Adjustment	Mid-year population estimate

1	Definition Number	3.2
----------	--------------------------	-----

2	Definition Name	Number of providers with a waiver under the Drug Addiction Treatment Act of 2000 (DATA 2000)
3	Data Sources	Drug Enforcement Administration's Active Controlled Substances Act (CSA) Registrants Database, which lists all provider types that meet the requirements to prescribe buprenorphine for the treatment of OUD; requires a purchased subscription from the National Technical Information Service (NTIS) ( https://classic.ntis.gov/products/dea/ )
4	Other Available Data for Additional or State-Specific Analyses	N/A
5	Primary Outcome Measure	Using information from the DEA's Active CSA Registrants Database, calculate the total number of buprenorphine for OUD treatment providers: (1) civilian physicians, (2) civilian nurse practitioners, and (3) civilian physician assistants
6	Population Size Adjustment	Mid-year population estimates
7	Strata	Measures will be stratified by level of prescribing

1	Definition Number	3.3
2	Definition Name	Number of providers with a DATA 2000 waiver who actively prescribe buprenorphine products that are FDA approved for OUD
3	Data Sources	
The calculation of this measure will require linkage between the DEA Active CSA Registrants Database and the state prescription drug monitoring program records to identify waivered prescribers from the HCS communities and their volume of prescriptions for buprenorphine products approved by FDA for the treatment of OUD.
 
Drug Enforcement Administration's Active Controlled Substances Act (CSA) Registrants Database, which lists all physicians who meet the requirements to prescribe buprenorphine for the treatment of OUD; requires a purchased subscription from NTIS (https://classic.ntis.gov/products/dea/) state prescription drug monitoring program records

4	Other Available Data for Additional or State-Specific Analyses	N/A

5	Primary Outcome Measure	Using information from the DEA's Active CSA Registrants Database, identify waivered prescribers (see measure 3.2) from the HCS communities and their allowed capacity (number of patients that they can treat at a given point)  Using the state prescription drug monitoring program records, for each prescriber in step 1, identify the unique patients who had at least one dispensed prescription issued by this prescriber for an FDA-approved buprenorphine product for treatment of OUD during the period under surveillance.  Calculate the total number of prescribers who prescribed buprenorphine to at least one patient
6	Population Size Adjustment	The denominator would be the “number of providers with a DATA 2000 waiver” (measure 3.2)
7	Strata	Measures will be stratified by level of prescribing

1	Definition Number	3.4
2	Definition Name	Number of providers who actively prescribe buprenorphine products that are FDA approved for OUD
3	Data Sources	Prescription Drug Monitoring Program (PDMP) data
4	Other Available Data for Additional or State-Specific Analyses	None
5	Primary Outcome Measure	Number of dispensed prescriptions with National Drug Code (NDC) for buprenorphine products that are approved by the FDA for the treatment of OUD.

1	Definition Number	3.5
2	Definition Name	Number of jails initiating and linking people to MOUD
3	Data Sources	De novo
4	Other Available Data for Additional or State-Specific Analyses	None
5	Primary Outcome Measure	1. Number of jails associated with HCS communities that initiate buprenorphine/methadone/Vivitrol for inmates before release 2. Number of jails associated with HCS communities that link people to MOUD treatment after release 3. Number of jails that provide naloxone to people upon release

1	Definition Number	3.8
2	Definition Name	Number of take-back drug drop boxes
3	Data Sources	All states will use DEA records to get the number of current drop boxes.
4	Other Available Data for Additional State-Specific Analyses	None
5	Primary Outcome Measure	Count of drug take-back boxes in HCS Communities

1	Definition Number	4.1.1
2	Definition Name	Number of ED visits for BH (count visits)
3	Population	Medicaid beneficiaries
4	Data Sources	Medicaid administrative data
5	Other Available Data for Additional or State-Specific Analyses	Claims (Medicaid in Kentucky, all-payer in Massachusetts and New York, combined Medicaid and OhioMHAS in Ohio; OASAS in New York; BSAS in Massachusetts)
6	Primary Outcome Measure	Count the number of unique emergency department (ED) visits with a behavioral health (BH) diagnosis code in the measurement period
7	Population Size Adjustment	Count of HCS residents who are Medicaid enrollees aged 18–64 who are non-dual eligible during the measurement period

1	Definition Number	4.1.2
2	Definition Name	Number of ED visits for non-BH (count visits)
3	Population	Medicaid beneficiaries
4	Data Sources	Medicaid administrative data
5	Other Available Data for Additional or State-Specific Analyses	Claims (Medicaid in Kentucky, all-payer in Massachusetts and New York, combined Medicaid and OhioMHAS in Ohio; OASAS in New York; BSAS in Massachusetts)
6	Primary Outcome Measure	Count the number of unique emergency department visits that do not have a behavioral health diagnosis code in the measurement period

7	Population Size Adjustment	Count of HCS residents who are Medicaid enrollees aged 18–64 who are non-dual eligible during the measurement period
----------	-----------------------------------	--

1	Definition Number	4.2.1
2	Definition Name	Number of hospital/inpatient nights for non-detox BH (count nights)
3	Population	Medicaid beneficiaries
4	Data Sources	Medicaid administrative data
5	Other Available Data for Additional or State-Specific Analyses	Claims (Medicaid in Kentucky, all-payer in Massachusetts and New York, combined Medicaid and OhioMHAS in Ohio; OASAS in New York; BSAS in Massachusetts)
6	Primary Outcome Measure	Count the number of inpatient nights with a behavioral health diagnosis code, excluding inpatient stays with a detox revenue or procedure code, in the measurement period
7	Population Size Adjustment	Count of HCS residents who are Medicaid enrollees aged 18–64 who are non-dual eligible during the measurement period

1	Definition Number	4.2.2
2	Definition Name	Number of hospital/inpatient nights for detox (count nights)
3	Population	Medicaid beneficiaries
4	Data Sources	Medicaid administrative data
5	Other Available Data for Additional or State-Specific Analyses	Claims (Medicaid in Kentucky, all-payer in Massachusetts and New York, combined Medicaid and OhioMHAS in Ohio; OASAS in New York; BSAS in Massachusetts)
6	Primary Outcome Measure	Count the number of detox inpatient nights in the measurement period
7	Population Size Adjustment	Count of HCS residents who are Medicaid enrollees aged 18–64 who are non-dual eligible during the measurement period

1	Definition Number	4.2.3
2	Definition Name	Number of hospital/inpatient nights for non-BH (count nights)
3	Population	Medicaid beneficiaries
4	Data Sources	Medicaid administrative data

5	Other Available Data for Additional or State-Specific Analyses	Claims (Medicaid in Kentucky, all-payer in Massachusetts and New York, combined Medicaid and OhioMHAS in Ohio; OASAS in New York; BSAS in Massachusetts)
6	Primary Outcome Measure	Count the number of inpatient nights that are NOT behavioral health in nature in the measurement period
7	Population Size Adjustment	Count of HCS residents who are Medicaid enrollees aged 18–64 who are non-dual eligible during the measurement period

1	Definition Number	4.3.1
2	Definition Name	Number of non-detox BH residential nights (count nights)
3	Population	Medicaid beneficiaries
4	Data Sources	Medicaid administrative data
5	Other Available Data for Additional or State-Specific Analyses	Claims (Medicaid in Kentucky, all-payer in Massachusetts and New York, combined Medicaid and OhioMHAS in Ohio; OASAS in New York; BSAS in Massachusetts)
6	Primary Outcome Measure	Count the number of residential non-detox nights, excluding the number of detox nights, in the measurement period; residential services by nature are assumed to be behavioral health related
7	Population Size Adjustment	Count of HCS residents who are Medicaid enrollees aged 18–64 who are non-dual eligible during the measurement period

1	Definition Number	4.3.2
2	Definition Name	Number of BH detox residential nights (count nights)
3	Population	Medicaid beneficiaries
4	Data Sources	Medicaid administrative data
5	Other Available Data for Additional or State-Specific Analyses	Claims (Medicaid in Kentucky, all-payer in Massachusetts and New York, combined Medicaid and OhioMHAS in Ohio; OASAS in New York; BSAS in Massachusetts)
6	Primary Outcome Measure	Count the number of residential detox nights in the measurement period; residential services by nature are assumed to be behavioral health related
7	Population Size Adjustment	Count of HCS residents who are Medicaid enrollees aged 18–64 who are non-dual eligible during the measurement period

1	Definition Number	4.4.1
2	Definition Name	Number of intensive BH outpatient visits (count nights)
3	Population	Medicaid beneficiaries
4	Data Sources	Medicaid administrative data
5	Other Available Data for Additional or State-Specific Analyses	Claims (Medicaid in Kentucky, all-payer in Massachusetts and New York, combined Medicaid and OhioMHAS in Ohio; OASAS in New York; BSAS in Massachusetts)
6	Primary Outcome Measure	Count the number of intensive outpatient visits in the measurement period; intensive outpatient visits by nature are assumed to be behavioral health related
7	Population Size Adjustment	Count of HCS residents who are Medicaid enrollees aged 18–64 who are non-dual eligible during the measurement period

1	Definition Number	4.5.1
2	Definition Name	Number of outpatient visits BH (count visits)
3	Population	Medicaid beneficiaries
4	Data Sources	Medicaid administrative data
5	Other Available Data for Additional or State-Specific Analyses	Claims (Medicaid in Kentucky, all-payer in Massachusetts and New York, combined Medicaid and OhioMHAS in Ohio; OASAS in New York; BSAS in Massachusetts)
6	Primary Outcome Measure	Count the number of outpatient visits with a behavioral health diagnosis code in the measurement period
7	Population Size Adjustment	Count of HCS residents who are Medicaid enrollees aged 18–64 who are non-dual eligible during the measurement period

1	Definition Number	4.5.2
2	Definition Name	Number of outpatient visits non-BH (count visits)
3	Population	Medicaid beneficiaries
4	Data Sources	Medicaid administrative data
5	Other Available Data for Additional or State-Specific Analyses	Claims (Medicaid in Kentucky, all-payer in Massachusetts and New York, combined Medicaid and OhioMHAS in Ohio; OASAS in New York; BSAS in Massachusetts)

6	Primary Outcome Measure	Count the number of outpatient visits that do NOT have a behavioral health diagnosis code in the measurement period
7	Population Size Adjustment	Count of HCS residents who are Medicaid enrollees aged 18–64 who are non-dual eligible during the measurement period

1	Definition Number	4.6.1
2	Definition Name	Number of non-pain buprenorphine days supplied (count days supply)
3	Population	Medicaid beneficiaries
4	Data Sources	Medicaid administrative data
5	Other Available Data for Additional or State-Specific Analyses	Claims (Medicaid in Kentucky, all-payer in Massachusetts and New York, combined Medicaid and OhioMHAS in Ohio; OASAS in New York; BSAS in Massachusetts)
6	Primary Outcome Measure	Count the number of days supplied of non-pain oral buprenorphine in the measurement period; this will come from two datasets: prescription drug claims and outpatient claims
7	Population Size Adjustment	Count of HCS residents who are Medicaid enrollees aged 18–64 who are non-dual eligible during the measurement period

1	Definition Number	4.6.2
2	Definition Name	Number of non-pain buprenorphine injections (count injections)
3	Population	Medicaid beneficiaries
4	Data Sources	Medicaid administrative data
5	Other Available Data for Additional or State-Specific Analyses	Claims (Medicaid in Kentucky, all-payer in Massachusetts and New York, combined Medicaid and OhioMHAS in Ohio; OASAS in New York; BSAS in Massachusetts)
6	Primary Outcome Measure	Count the number of non-pain buprenorphine injections in the measurement period; this will come from two datasets: outpatient claims and prescription drug claims.
7	Population Size Adjustment	Count of HCS residents who are Medicaid enrollees aged 18–64 who are non-dual eligible during the measurement period

1	Definition Number	4.6.3
----------	--------------------------	-------

2	Definition Name	Number of opioid-related oral naltrexone days supplied (count days supply)
3	Population	Medicaid beneficiaries
4	Data Sources	Medicaid administrative data
5	Other Available Data for Additional or State-Specific Analyses	Claims (Medicaid in Kentucky, all-payer in Massachusetts and New York, combined Medicaid and OhioMHAS in Ohio; OASAS in New York; BSAS in Massachusetts)
6	Primary Outcome Measure	Count the number of prescription days supplied that are opioid related oral naltrexone fills in the measurement period; the population in the denominator for this measure requires evidence (i.e., a diagnosis) of an OUD in the measurement period or in the past 12 months
7	Population Size Adjustment	Count of HCS residents who are Medicaid enrollees aged 18–64 who are non-dual eligible during the measurement period

1	Definition Number	4.6.4
2	Definition Name	Number of opioid-related naltrexone injections (count injections)
3	Population	Medicaid beneficiaries
4	Data Sources	Medicaid administrative data
5	Other Available Data for Additional or State-Specific Analyses	Claims (Medicaid in Kentucky, all-payer in Massachusetts and New York, combined Medicaid and OhioMHAS in Ohio; OASAS in New York; BSAS in Massachusetts)
6	Primary Outcome Measure	Count the number of opioid related naltrexone injections in the measurement period; this will come from two datasets: outpatient claims and prescription drug claims. The population in the denominator for this measure requires evidence (i.e., a diagnosis) of an OUD in the measurement period or in the past 12 months.
7	Population Size Adjustment	Count of HCS residents who are Medicaid enrollees aged 18–64 who are non-dual eligible during the measurement period

1	Definition Number	4.6.5
2	Definition Name	Number of methadone days supplied (count calculated days supply)
3	Population	Medicaid beneficiaries

4	Data Sources	Medicaid administrative data
5	Other Available Data for Additional or State-Specific Analyses	Claims (Medicaid in Kentucky, all-payer in Massachusetts and New York, combined Medicaid and OhioMHAS in Ohio; OASAS in New York; BSAS in Massachusetts)
6	Primary Outcome Measure	Count the number of days that methadone has been supplied in the measurement period
7	Population Size Adjustment	Count of HCS residents who are Medicaid enrollees aged 18–64 who are non-dual eligible during the measurement period

1	Definition Number	4.7.1
2	Definition Name	Number of opioid pain medication days supplied (count days supply)
3	Population	Medicaid beneficiaries
4	Data Sources	Medicaid administrative data
5	Other Available Data for Additional or State-Specific Analyses	Claims (Medicaid in Kentucky, all-payer in Massachusetts and New York, combined Medicaid and OhioMHAS in Ohio; OASAS in New York; BSAS in Massachusetts)
6	Primary Outcome Measure	Count the number of prescription days supplied that are opioid pain medication fills in the measurement period
7	Population Size Adjustment	Count of HCS residents who are Medicaid enrollees aged 18–64 who are non-dual eligible during the measurement period

1	Definition Number	4.7.2
2	Definition Name	Number of non-opioid pain medication days supplied (count days supply)
3	Population	Medicaid beneficiaries
4	Data Sources	Medicaid administrative data
5	Other Available Data for Additional or State-Specific Analyses	Claims (Medicaid in Kentucky, all-payer in Massachusetts and New York, combined Medicaid and OhioMHAS in Ohio; OASAS in New York; BSAS in Massachusetts)
6	Primary Outcome Measure	Count the number of prescription days supplied that are non-opioid pain medication fills in the measurement period
7	Population Size Adjustment	Count of HCS residents who are Medicaid enrollees aged 18–64 who are non-dual eligible during the measurement period

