N/A	Number of individuals linked to MOUD after release from prison	2.10	Medicaid administrative data, including claims and eligibility files linked to incarcerated individual files from state departments of corrections
N/A	Number of individuals provided MOUD while in jail	2.11	Primary data collection—survey ( Justice Community Opioid Innovation Network [JCOIN] and HCS Annual Jail Survey )
N/A	Number of individuals linked to MOUD after an opioid-related ED visit	2.12	Medicaid administrative data, including claims and eligibility files
N/A	Number of individuals with OUD who are screened, diagnosed, and treated for hepatitis C	2.15	Medicaid administrative data, including claims and eligibility files
N/A	Number of newly diagnosed HIV cases	2.16	State registry for HIV/AIDS reporting
N/A	Number of opioid-related overdoses treated in EDs and captured by syndromic surveillance data	2.17	Syndromic surveillance records (accessed via the Centers for Disease Control and Prevention's National Syndromic Surveillance Program Electronic Surveillance System for the Early Notification of Community-based Epidemics (NSSP-ESSENCE) application or other state-based platforms)

Hypothesis	Associated Outcomes	Appendix A Reference Number	Data Source
N/A	Number of new acute opioid prescriptions limited to a 7-day supply	2.18	Prescription drug monitoring program
N/A	Opioid prescriptions from multiple prescribers or pharmacies	3.1	Prescription drug monitoring programs
N/A	Number of providers with a waiver under the Drug Addiction Treatment Act of 2000 (DATA 2000)	3.2	U.S. Drug Enforcement Administration's (DEA) Active Controlled Substances Act (CSA) Registrants Database
N/A	Number of providers with a DATA 2000 waiver who actively prescribe buprenorphine products that are FDA approved for OUD	3.3	DEA's Active CSA Registrants Database linked to prescription drug monitoring program data
N/A	Number of providers who actively prescribe buprenorphine products that are FDA approved for OUD	3.4	Prescription Drug Monitoring Program (PDMP) data
N/A	Number of jails initiating and linking people to MOUD	3.5	Primary data collection—survey ( Justice Community Opioid Innovation Network [JCOIN] and HCS Annual Jail Survey )
N/A	Number of take-back drug drop boxes and events	3.8	State administrative data and DEA's Active CSA Registrants Database
N/A	Number of ED visits for BH (count visits)	4.1.1	Medicaid administrative data, including claims and eligibility files

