#### **9.4.3 Analysis of the Secondary Outcomes**

As with the primary outcome, secondary and structural outcomes will be modeled using an ITT approach as described above. The models will include trial arm as the main independent variable and will control for the following covariates: the RS (i.e., Kentucky, Massachusetts, New York, or Ohio), the rural/urban status of the community, baseline opioid overdose death rate, and the observed baseline level of the particular secondary outcome for the community. The secondary outcomes related to H2–H4 in Section 9.1 are counts or rates; therefore, a marginal negative binomial regression model estimated using GEE will be utilized to analyze the count outcomes, as with the primary analysis. For those outcomes that involve a rate, the implied denominator in the county during the 12-month parallel-arm trial period will be utilized to offset the model, such that the outcome is interpreted as a rate, and differences between treatment assignments would be rate ratios. A model-based approach will be used for hypothesis testing, as described in the primary analysis.

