5	Other Available Data for Additional or State-Specific Analyses	Claims (Medicaid in Kentucky, all-payer in Massachusetts and New York, combined Medicaid and OhioMHAS in Ohio; OASAS in New York; BSAS in Massachusetts)
6	Primary Outcome Measure	Count of individuals receiving methadone as MOUD during the measurement period
7	Population Size Adjustment	Count of HCS residents who are Medicaid enrollees aged 18–64, with OUD receiving MOUD during the measurement period

1	Definition Number	2.5.3
2	Definition Name	Number of individuals receiving naltrexone
3	Population	Medicaid beneficiaries
4	Data Sources	Medicaid administrative data
5	Other Available Data for Additional or	All-payer claims (Massachusetts)

	State-Specific Analyses	
6	Primary Outcome Measure	Count of individuals receiving naltrexone as MOUD during the measurement period
7	Population Size Adjustment	Count of HCS residents who are Medicaid enrollees aged 18–64, with OUD receiving MOUD during the measurement period

1	Definition Number	2.5.4
2	Definition Name	Number of individuals with OUD receiving MOUD
3	Population	Medicaid beneficiaries
4	Data Sources	Medicaid administrative data
5	Other Available Data for Additional or State-Specific Analyses	All-payer claims (Massachusetts and New York); Ohio can combine claims from Medicaid and OhioMHAS; OASAS in New York; BSAS in Massachusetts
6	Primary Outcome Measure	Count of HCS residents who are Medicaid enrollees aged 18–64, with OUD receiving MOUD during the measurement period
7	Population Size Adjustment	Number of member-months enrolled during the 12-month study period for full-benefit Medicaid enrollees, aged 18–64, who were identified as individuals with OUD

1	Definition Number	2.6
2	Definition Name	Number of individuals with OUD receiving behavioral health treatment
3	Population	Medicaid beneficiaries
4	Data Sources	Medicaid administrative data
5	Other Available Data for Additional or State-Specific Analyses	All-payer claims (Massachusetts and New York); Ohio can combine claims from Medicaid and OhioMHAS; OASAS in New York; BSAS in Massachusetts

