6	Primary Outcome Measure	
2.6.1: Number of individuals with OUD receiving behavioral health treatment (inpatient, ASAM levels 3,4)
 
2.6.2: Number of individuals with OUD receiving behavioral health treatment (IOP, ASAM level 2)
 
2.6.3: Number of individuals with OUD receiving behavioral health treatment (outpatient, ASAM level 1)
 
2.6.4: Number of individuals with OUD receiving behavioral health treatment (any of ASAM levels 1–4)

		2.6.5 Number of individuals with OUD receiving behavioral health treatment (any of ASAM levels 1–4) 2.6.6: Number of individuals with OUD receiving behavioral health treatment (peer support) 2.6.7: Number of individuals with OUD receiving behavioral health treatment (any of case management, peer support) 2.6.8: Number of individuals with OUD receiving behavioral health treatment (screening)
7	Population Size Adjustment	Medicaid enrollees with a diagnosis of OUD and a claim for MOUD during the measurement period, recorded during any health service encounter (inpatient, outpatient, office visit, ED, etc.)

1	Definition Number	2.7.1
2	Definition Name	Number of individuals receiving buprenorphine/naloxone retained beyond 6 months
3	Population	General
4	Data Sources	Prescription drug monitoring programs
5	Other Available Data for Additional or State-Specific Analyses	Claims (Medicaid in Kentucky; all-payer in Massachusetts and New York, Medicaid/OhioMHAS in Ohio; OASAS in New York)
6	Primary Outcome Measure	Individuals who maintained continual MOUD for 6 months in the measurement period. Continuous treatment is calculated based on days' supply and dosage, and an individual can have a gap of no more than 7 days' treatment to be considered in continual treatment.
7	Population Size Adjustment	Mid-year population in the county or local community

1	Definition Number	2.7.2
2	Definition Name	Number of individuals receiving methadone retained beyond 6 months
3	Population	Medicaid beneficiaries
4	Data Sources	Medicaid beneficiaries
5	Other Available Data for Additional or State-Specific Analyses	All-payer claims in Massachusetts and New York; Ohio can combine claims from Medicaid and OhioMHAS; BSAS in Massachusetts

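### Outcome 3.4 is named a count of prescribers but defined as a count of dispensed prescriptions; the 2.6 adjustment row also adds an MOUD condition that its name lacks

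*Protocol*

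**What the plan says.** Outcome 3.4 has the same name in Protocol Table 2 and in Appendix A 12.1.3: "Number of providers who actively prescribe buprenorphine products that are FDA approved for OUD". Its data source is the prescription drug monitoring program (PDMP). Its Primary Outcome Measure is "Number of dispensed prescriptions with National Drug Code (NDC) for buprenorphine products that are approved by the FDA for the treatment of OUD", and no further counting step follows. The entry above it, 3.3, covers waivered providers and ends with an explicit step: "Calculate the total number of prescribers who prescribed buprenorphine to at least one patient".

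Outcome 2.6 (Appendix A 12.1.2) covers people with OUD in behavioral health treatment. Neither its name nor any of its eight sub-measures mentions MOUD. Its Population Size Adjustment is "Medicaid enrollees with a diagnosis of OUD and a claim for MOUD during the measurement period". By contrast, 2.5.4 and 2.7.5 are adjusted by "Number of member-months enrolled during the 12-month study period for full-benefit Medicaid enrollees, aged 18–64, who were identified as individuals with OUD".

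Outcomes 2.5.2 (methadone) and 2.5.3 (naltrexone) are adjusted by "Count of HCS residents who are Medicaid enrollees aged 18–64, with OUD receiving MOUD during the measurement period". The same words form the outcome measure of 2.5.4.

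On the use of these rows, Protocol 9.4.3 says: "For those outcomes that involve a rate, the implied denominator in the county during the 12-month parallel-arm trial period will be utilized" as an offset. It does not list which outcomes those are. The SAP was narrowed to opioid overdose deaths (SAP 1.3, version 1.1), so it settles none of this.

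**The concern.** A name tells the reader what an estimate means, and the measure row tells the programmer what to compute. For 3.4 the two have different units. Outcomes 3.2 and 3.3 both depend on the DATA 2000 waiver, so 3.4 is the only listed outcome that could count active buprenorphine prescribers regardless of waiver. As written it does not do so, and a result on prescribing volume could be reported as a change in the number of prescribers.

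For 2.6 the issue is whether the numerator sits inside the denominator. Dividing all people with OUD in behavioral treatment by only those with an MOUD claim gives neither a proportion nor a rate among people with OUD. Expanding MOUD is also an aim of the intervention (Protocol 6.1.1.4), so this denominator could differ between arms for reasons unrelated to behavioral treatment.

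**Working it through.** The documents give no figure for these outcomes, so there is nothing to reproduce. The check compares each name with its measure and adjustment row, then shows the consequence on assumed inputs. Ratios are Wave 1 relative to Wave 2.

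**Outcome 3.4**

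- Unit in the name: providers. Unit in the measure: dispensed prescriptions. This mismatch needs no assumption.
- Prescription ratio = prescriber ratio × ratio of prescriptions per prescriber.
- Assume 20% more prescribers. The prescription ratio is below 1 when prescriptions per prescriber fall by more than 1 − 1/1.20 = 16.7%.
- Assume 10% fewer prescribers. The prescription ratio is above 1 when prescriptions per prescriber rise by more than 1/0.90 − 1 = 11.1%.
- Example: 12 prescribers × 20 patients × 12 fills = 2,880 prescriptions, against 10 × 30 × 12 = 3,600. The prescriber ratio is 12/10 = 1.20 and the prescription ratio is 2,880/3,600 = 0.80.

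**Outcome 2.6, if its row is the denominator**

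- Let b be the fraction of enrollees with OUD in behavioral treatment and a the fraction with an MOUD claim. The computed level is b/a, which exceeds 1 whenever b > a.
- Assume b from 0.40 to 0.70 and a from 0.40 to 0.60. The level runs from 0.40/0.60 = 0.67 to 0.70/0.40 = 1.75.
- Hold b at 0.50. At a = 0.20, 0.40, 0.50 and 0.60 the level is 2.50, 1.25, 1.00 and 0.83, although behavioral treatment has not changed.
- As an arm comparison, with b = 0.50 in both arms, a = 0.50 in Wave 1 and a = 0.40 in Wave 2, the ratio is 1.00/1.25 = 0.80. Per person with OUD it would be 0.50/0.50 = 1.00.

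**Outcomes 2.5.2 and 2.5.3, if their row is the offset**

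- The quantity is the drug's share of MOUD recipients. Let s be the drug's share at baseline, m the count ratio for the named drug and o the count ratio for other MOUD, with no overlap between drugs. The crude share ratio is m / [(1 − s)·o + s·m].
- With m = 1.10, o = 1.30 and s = 0.35: 1.10 / (0.65 × 1.30 + 0.35 × 1.10) = 1.10/1.23 = 0.89. Over all values of s it lies between 1.10/1.30 = 0.85 and 1.00.
- More people on the drug can therefore appear as a ratio below 1. That is correct for a share but would mislead under the present name.

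**The case against.** On 3.4, the measure row may only be a record filter for the qualifying drug codes, with the prescriber count left out by oversight. The name is the same in both places, Appendix A describes itself as brief (Protocol 10.1.8.1), and SAP 6.1 refers to separate technical specifications, there for outcome 1. An omission is at least as likely as an intended prescription count, so the point concerns the text and not what analysts did. The text still needs correcting: Protocol 10.1.8.1 places the operational definitions in Appendix A, and 3.3 spells out the step that 3.4 lacks.

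On 2.6, 2.5.2 and 2.5.3, the strongest defence is the context in Protocol 9.4.3. The offset sentence directly follows one limited to the outcomes for H2–H4, and those are all adjusted by mid-year population. Without an offset, the raw counts match their names. A wider reading is possible: the section opens by covering all secondary and structural outcomes, and Appendix A states that the row of the same name is the offset for outcome 1. The documents do not decide between the two readings, so this part stays conditional.

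Appendix A also often pairs a count name with a restricted denominator, as in 3.3, 2.9, 2.10 and 2.12. That defence holds for 2.5.2 and 2.5.3, where a drug's share of MOUD recipients is a legitimate measure. It does not help 2.6, because those other denominators contain their numerators and this one does not.

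A reader might infer that methadone and naltrexone uptake will be misestimated. The documents do not support this, since use of the row as an offset is not established. A reader might also infer that multiplying the share ratio by the 2.5.4 ratio recovers the change in recipients. That identity holds for crude ratios with equal OUD member-months in the arms. Protocol 9.4.3 fits separate negative binomial models, each adjusted for its own baseline level, and the product of two such estimates need not equal a direct one.

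**Conclusion.** Outcome 3.4 is wrong as written: its name and its only stated measure have different units, and on plausible inputs they can point in opposite directions. The 2.6 adjustment row does not match the population in its name. That matters only if the row is the denominator, in which case the ratio can exceed 1 and falls as MOUD expands. For 2.5.2 and 2.5.3 the point is one of labelling, and only if the row is used.

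The reach is limited. All these outcomes are listed in Table 2 without a hypothesis; H1–H4 and the power calculation are untouched. Every growth figure and share above is an assumption chosen to show direction. The technical specifications were not seen and may already define 3.4 correctly, but the protocol text would still need to agree with them.

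**What to change.** - **3.4:** define the measure as the number of distinct prescribers with at least one dispensed prescription, in the period, for a buprenorphine product FDA-approved for OUD. Use the PDMP data already listed and follow the counting step of 3.3. State how a prescriber is assigned to a community, because 3.3 takes this from the DEA registrants database, which 3.4 does not list.
- **2.6:** replace the adjustment row with an OUD denominator that has no MOUD condition, such as the member-months used for 2.5.4 and 2.7.5. Note beside it that OUD identified from claims may itself respond to the intervention.
- **2.5.2 and 2.5.3:** state whether the row is an offset. If it is, label the result as the drug's share of MOUD recipients.
- Align the technical specifications with the revised text.

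The cost is a protocol amendment with IRB review (Protocol, Statement of Compliance). State partners may also have to re-query counts: Massachusetts supplies only summary statistics for non-death data, with small-number suppression, and New York transfers only aggregates (Protocol 10.1.8.1). Any change now comes after the evaluation period, which ended in June 2022. Outcome 3.4 was itself added in August 2023 (Protocol 10.3), so the amendment should record the date and reason.
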